7.1 Handling of Dropouts or Missing Data

All participants should be included in the analysis regardless of missing values and no imputation (for example, last value carried forward) should be utilised. All possible care should be taken to ensure that missing values are not encountered at baseline especially with respect to subgroups of interest. The analysis methods to be suggested in the following section take into account all available data and produce unbiased estimates of effect even in the presence of missing values.

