5.2.2.4 Routine speech discrimination assessment in quiet

As is performed routinely, assessment of speech recognition in quiet, is performed and the results recorded **at preimplant and post implant visits in the subject's daily listening condition, i.e.:**

- aided binaurally or
- aided monaurally, one ear unaided, or
- bilaterally unaided (i.e. no hearing aid available at preimplant assessment, only in cases with clinical record of a recent unsuccessful hearing aid trial).

As per local routine practices, standardly used speech materials are presented in the sound field at varied presentation levels, to determine the speech intensity function curve per individual, which includes 65 dB SPL. Recorded speech stimuli are presented from a loud speaker at 0° Azimuth, 1 meter away at head level. Speech test materials may include monosyllabic or disyllabic word lists in the native language.

Recorded outcomes will include the percent of items correctly identified compared to the total number of speech items presented at 65dB SPL and the speech reception threshold level,

dBSPL, at which 50% of speech items are correctly recognized, i.e. SRT50%. This routine test is completed in approximately 10 to 15 minutes by the clinician together with the candidate/recipient.

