5.2.2.5 Routine speech discrimination assessment in noise

As is performed routinely, assessment of speech recognition in noise, is performed and the results recorded **at preimplant and post implant visits in the subject's daily listening condition, i.e.:**

- aided binaurally or
- aided monaurally, one ear unaided.

Tests in noise are typically done for patients who can correctly understand a minimum of 50% of speech items in quiet. Speech tests are performed in the free field sound booth with competing background NOISE. According to local routine practices, standardly used speech materials are presented in the sound field at adaptively to obtain the SRT50% in noise, OR speech stimuli may presented fixed at 65 dB SPL and the competing background noise (i.e. pink noise) varied for each presentation list to obtain the SRT50%. Recorded speech stimuli and the competing background noise are presented from a loud speaker at 0° Azimuth, 1 meter away at head level. Test materials may include sentences or words as is typically used in the native language.. This routine test is completed in approximately 10 to 15 minutes by the clinician together with the candidate/recipient.

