8.2 Overview to Assessment Schedule and Visits

Figure 3 below represents an overview of the evaluation visits for each enrolled subject, designed to coincide with routine clinical visits involved in provision of CI intervention. Each subject will be assessed during three visits while participating in the study, creating three data sets and evaluation points per subject. The full battery of tests will be repeated at each of the three visits.

[figure not shown]

Figure 3 Overview to evaluation schedule flow and visits for each enrolled subject.

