8.4 End-points

Primary end-point

Change in overall health related quality of life via comparison of HUI3 multi-attribute utility scores at:

- **Post1** implant Visit compared to **Pre1** implant Visit
- **Post2** implant Visit compared to **Post1** implant Visit
- **Post2** implant Visit compared to **Pre1** implant Visit

Secondary end-points:

Change in scores on battery of evaluation tools for health related domains and overall well-being on each of the following:

MMSE, DSST & Trail B (Cognition); TUG (falls); GDS-15 (depression); iADL (independency); HHIE-S (hearing handicap); SSQ (hearing & communication ability); CAP-II (capabilities of audition); De Jong Loneliness Scale, Speech recognition tests in Quiet (daily hearing function); Speech recognition tests in Noise (daily hearing function); Consistent daily use of CI via automatic data logging (hrs/day and listening environments).

- **Post1** implant Visit compared to **Pre1** implant Visit
- **Post2** implant Visit compared to **Post1** implant Visit
- **Post2** implant Visit compared to **Pre1** implant Visit

Tertiary end point:

Changes in healthcare resource utilisation with CI treatment compared to preimplant, collected at each test interval, i.e., Pre 1, Post1 and Post 2 will be compared. Each assessment will reflect a 6 month period immediately before assessment. Data reviewed for this measure will be obtained from the customized HRU questionnaire completed by the clinician on behalf of the subject (data sources available for use will be in accordance with regional guidelines).

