7.3 Statistical Analyses

Primary hypothesis analysis

If comparison between the HUI3 multi-attribute score from pre-surgery to only one follow-up time point is of interest then paired t-tests can be used. A check of the assumption that the change from pre-surgery is normally distributed should be performed. The distribution of change scores should be approximately symmetric. The disadvantage of this approach is that it uses only complete data at any given pair of time points

If all pairwise differences are of interest (as per the hypothesis) and the scatter plot of change over time appears (close to) linear then a linear mixed-effects model with a fixed effect of time (treated as a continuous variable) and a random effect for participant should be used to explain the change in response variable over time. Tukey pairwise differences between time points can be specified (we recommend using the *multcomp* package in R as it does not require balanced designs i.e. the same sample size across time points). Appropriate diagnostic checks of the linear mixed-effects model (for example, normality of the residuals, normality of the random effects) should always be undertaken. An advantage of the linear mixed-effects model is that it uses all available data even for subjects who have dropped out at a given time point and then returned.

If the change over time was evidently not linear from the scatterplot of response against time then alternative approaches should be used. For example:

1. A quadratic or cubic term for time could be added to the linear mixed-effects model and checked to determine if that improves the fit of the model (eg via reduced AIC, better diagnostic checks).
2. The pre-surgery HUI3 multi attribute score value can be used as a predictor variable (with the response variable then only including the post-surgery visits). A significant coefficient would imply that the amount of change is dependent on the pre-surgery score. An interaction between baseline score and post-surgery time points could also be included – this would show whether the change in mean score over time is impacted by baseline score. This approach will remove any participant without baseline data from the analysis.

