3. Use visit as categorical variable. This essentially fits a linear model between time points but makes no assumption that the change from baseline is linear. Tukey pairwise comparisons between all pairs of time points (if time is found to be a significant predictor) are straight forward with this approach and should be undertaken using the *multcomp* package in R, which does not require balanced designs.

Secondary hypotheses analysis

The approach described for the primary hypothesis can be used for all continuous responses described in the secondary hypotheses. Failure of the assumptions may indicate that that a linear model is not appropriate and that other response distributions need to be explored. At this stage it is likely best that a statistician is consulted.

For ordinal responses such as the CAP II score an ordinal mixed-effects model including time as a fixed effect and participant as a random effect. The results of this model will show the

odds of being in a higher category compared to the current category over time (this interpretation is package dependent).

Tertiary hypotheses analysis

The approach described for the primary hypothesis is appropriate here also for continuous outcomes. As described above, for ordinal responses an ordinal mixed-effects model including time as a fixed effect and participant as a random effect. If the response variable is nominal (categorical without natural ordering) a multinomial mixed-effects model can be used and for binary responses a mixed effects logistic regression can be undertaken.

If only one pair of time points is of interest then for binary responses a test for the change in proportions can be undertaken and for continuous responses a paired t-test can be undertaken.

Analysis for other hypotheses

The other hypotheses involve the effect of covariates on a response and on the change over time. To assess the effect of a given covariate (for example age, gender, etc) the covariate can be added to the model as a fixed main effect in addition to the time variable and as an interaction with the time variable.

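### SAP 7.1 promises unbiased estimates with missing data and states no condition; speech in noise and removal for health decline are two routes by which the needed condition may fail

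*SAP*

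**What the plan says.** SAP 7.1 includes every participant whatever is missing, rules out imputation, asks for care to avoid missing baseline values, and states that the methods of the next section "produce unbiased estimates of effect even in the presence of missing values". It names no missing-data mechanism and plans no sensitivity analysis.

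For the all-pairwise hypothesis, SAP 7.3 (Statistical Analyses) gives "a linear mixed-effects model with a fixed effect of time (treated as a continuous variable) and a random effect for participant", with visit as a categorical variable among the fallbacks. It also lists a paired t-test and a model with the pre-surgery score as predictor. It says itself that the first uses only complete pairs and that the second loses anyone without a baseline. For secondary endpoints, "The approach described for the primary hypothesis can be used for all continuous responses described in the secondary hypotheses".

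Speech in noise is a secondary change endpoint against Pre1 (Protocol 8.4). Protocol 5.2.2.5 says: "Tests in noise are typically done for patients who can correctly understand a minimum of 50% of speech items in quiet". Its listening conditions leave out the case with neither ear aided, which Protocol 5.2.2.4 allows for quiet before implant. Yet Protocol 8.2 says "The full battery of tests will be repeated at each of the three visits", and the synopsis schedule and Table 2 (Protocol 8.3) list the noise test at all three visits.

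On dropout, Protocol 8.6.7 expects 5 to 10% loss and calls it random. Protocol 8.6.3 lets the investigator discontinue a subject for rapid health decline, and Protocol 17 asks the clinician to remove a subject whose declining health prevents comfortable participation.

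**The concern.** A likelihood-based mixed model does not deliver unbiasedness unconditionally. The reason for a missing value must be explained by data that the model uses, and the model must be right. The documents themselves describe two mechanisms that may not meet this.

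- **Speech in noise.** Whether a noise score exists depends on the quiet score at the same visit. The model has only time and participant, so the variable that drives the gap is outside it. The subjects are cochlear implant candidates, so failing the gate is most likely at Pre1. Those who move from untestable to testable may be among those who gain most.
- **HUI3.** Subjects removed because their health declined probably have worse unseen scores than those who stay, which would inflate the estimated gain in the primary endpoint.

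Because SAP 7.1 says that missing values do no harm, it gives an analyst no reason to look at either.

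**Working it through.** **The plan's own figures.** With a change of 0.1, an SD of change of 0.25, a two-sided paired t-test and 90% power (SAP 5, Protocol 9), the exact noncentral-t calculation gives N = 68 at 0.05 and N = 88 at 0.05/3. Both match the SAP. With 100 enrolled and 10% lost, 100 × 0.90 = 90 remain, with power of about 91% at 0.0167. Planned power survives the expected loss, so the question is bias.

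**Speech in noise, threshold score.** The documents give no testable share and no correlations, so these are assumptions.

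- Set-up: normal quiet and noise scores at three visits, scaled so that higher is better; 85% testable at both post-implant visits; a noise score is missing when the quiet score is below the gate.
- Analysis: maximum-likelihood random-intercept model with categorical visit, 200,000 subjects per setting. Quiet–noise and between-visit correlations are 0.5 unless stated.

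| Testable before implant | Below-gate subjects tested anyway | Gain understated by (SD) |
|---|---|---|
| 15% | none | 0.47 |
| 30% | none | 0.33 |
| 50% | none | 0.20 |
| 30% | 30% | 0.11 |
| 30% | 50% | 0.05 |
| 30% | 70% | 0.02 |

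At 30% testable with an absolute gate, correlations of 0.3 to 0.7 give 0.13 to 0.56 SD. Across 15 to 50% testable the range is 0.08 to 0.81 SD.

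The share without a Pre1 noise score at 30% testable is 70% under an absolute gate. It is 0.70 × 0.70 = 49%, 0.70 × 0.50 = 35% or 0.70 × 0.30 = 21% if 30, 50 or 70% of below-gate subjects are tested anyway.

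At trial size (N = 95, 7.5% loss, 30% testable), a true gain of 0.8 SD is estimated as 0.47 under an absolute gate (0.80 − 0.47 = 0.33) and as 0.69 with 30% tested anyway (0.80 − 0.69 = 0.11).

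Complete pairs are less biased here than the mixed model: 0.26 against 0.33 SD at 30% testable with an absolute gate.

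**Speech in noise, percent correct** (the other outcome in SAP 6). With an assumed true gain of 30 points from a mean of 15 to 25% and an absolute gate, the gain is understated by 2.0 to 4.6 points at 30% testable and correlations of 0.5. Over all settings the result runs from about 1 point overstated to 14 understated, so near the floor the direction is not settled.

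**HUI3.** The inputs are a mean change of 0.165 in the earlier data set (Protocol 9) and a loss of 5 to 10% (Protocol 8.6.7). The health-related share of the loss and the mean change c in those lost are assumed.

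Overstatement = loss × health-related share × (0.165 − c)

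- Low: 0.05 × 0.5 × (0.165 − 0) = 0.004
- High: 0.10 × 0.5 × (0.165 + 0.20) = 0.018
- All loss health-related: 0.10 × 1 × 0.365 = 0.037

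A random-intercept simulation gives 0.004 to 0.019 with equal baselines and half the loss health-related. It gives 0.002 to 0.025 if those lost started 0.2 lower to 0.1 higher, and up to 0.050 if all loss is health-related and they started 0.2 lower.

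A separate simulation linked dropout to the unseen 12-month score, with a true change of 0.10. It gave 0.008 to 0.018 under a moderate link. When the lowest scorers are all lost, it gave 0.018 to 0.022 at 5% loss and 0.033 to 0.039 at 10%.

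The documents' own yardstick is the 0.03 important change (Protocol 5.2.1 and 9).

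Tipping point at 10% loss: for an observed 0.165 to fall to 0.10, those lost would need a mean change of (0.10 − 0.9 × 0.165) / 0.10 = −0.485.

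**The case against.** Several objections are fair.

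- **The gate is not absolute.** Protocol 5.2.2.5 says *typically*, the test is scheduled at every visit, and SAP 7.1 asks for care over baseline values. A reader might infer that below-gate subjects have no baseline score. The documents support only that many may lack one, and the bias shrinks quickly as more of them are tested. This stands, and the 0.33 SD must be read with it.
- **The sentence need not fail mainly for speech in noise.** That is one secondary endpoint, and for the threshold score the bias understates benefit. Health-decline removal touches the primary endpoint and flatters it. The documents do not support a ranking.
- **Dropping subjects without baseline does not make speech in noise worse.** That inference is tempting, but complete pairs were less biased than the mixed model. The complete-case options contradict the all-data claim in SAP 7.1, and SAP 7.3 discloses their limits openly.
- **The model for this outcome is not fixed.** SAP 7.3 says the primary approach *can* be used, and SAP 6 leaves the distribution open until data are seen. This is true, but neither place mentions the gate.
- **Some details may lie elsewhere.** The separate procedure document (Protocol 8.7) and the case report forms were not available and may already code untestable subjects. The fix allows for this.
- **The unaided-in-both-ears gap is small.** Protocol 5.2.2.4 limits that condition to subjects with a recorded recent failed hearing-aid trial, and no number is given.

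None of this rescues the unconditional sentence in SAP 7.1.

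**Conclusion.** The statement in SAP 7.1 is wrong as written and should be corrected. Its unbiasedness holds only under missing at random given the data in the model and a correct model, and its all-data claim conflicts with two options in SAP 7.3.

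For speech in noise, the threshold gain may be understated by anything from about 0.02 SD to about 0.33 SD at 30% testable and correlations of 0.5, depending mainly on how strictly sites apply the gate. Other assumed shares and correlations widen this. For percent correct the direction is uncertain.

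For HUI3, the gain may be overstated by about 0.004 to 0.018 if half of the 5 to 10% loss is health-related. Only extreme assumptions (0.037 to 0.050) pass 0.03. A reader might infer that the primary result is unsafe. The documents' figures do not support that: the primary conclusion is probably safe. It remains unclear whether the random loss in Protocol 8.6.7 is meant to include removals for health decline.

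Confidence is high that the sentence needs a condition. It is only medium on the sizes, which rest on assumed testable shares, correlations and dropout mechanisms.

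**What to change.** 1. **Reword SAP 7.1.** Say that estimates are unbiased if data are missing at random given the observed data in the model and the model is correctly specified. Except the paired t-test and the baseline-as-predictor option.
2. **Speech in noise.** Reconcile Protocol 5.2.2.5 with 8.2 on who is tested, and with 5.2.2.4 on subjects with neither ear aided. If the forms do not already do so, record not testable (below 50% in quiet) separately from other missing values. Report the proportion testable at each visit beside the listed change in scores, and label that change as conditional on testability. Ranking untestable as worst and fitting "an ordinal mixed-effects model including time as a fixed effect and participant as a random effect", which SAP 7.3 already plans for ordinal responses, is optional. That result mixes testability with score: in simulation it was always significant when only testability rose. It must therefore be read beside the proportion testable.
3. **HUI3.** Add one delta-adjusted (tipping-point) sensitivity analysis for subjects with no post-implant score. Limit the no-imputation sentence in SAP 7.1 to the main analysis so that this is allowed.

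The cost is some SAP wording, possibly one extra code on the form, and a few short analyses. The HUI3 gain may look slightly smaller in the sensitivity analysis.

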7.2 Summary Statistics

In preliminary work, summary statistics and plots should be examined for each variable to be included in a given analysis at each time point. This helps to describe the population and identify potential issues with the data. Appropriate summaries include:

- For one categorical variable (such as CAPII, gender, work status, education level) the count and proportion of participants in each category of the given variable should be tallied and the mode could be identified. Bar charts should also be created.
- For one continuous or discrete (integer only) variable (for example HUI3 multi attribute score, out of pocket costs, smoking level, age) the mean, standard deviation, median and interquartile range (IQR) could be calculated. Boxplots and histograms can be used to summarise the continuous and discrete (including response) variables.
- Non-normality of a given response at any time point is not necessarily a problem since the analysis to be used does not make assumptions about the distribution of the response scores.

For the primary and secondary hypotheses

- The change in the response variable over time should be examined by using boxplots with the response as the y-axis and time as the grouping variable or using scatterplots with a longitudinal trend included. Each persons' observations could be joined to show the variability in individual response over time. The purpose of this is to determine whether a linear change over time is apparent. This will impact on the form of the analyses undertaken.

For the tertiary and other hypotheses

- For categorical predictors of interest, boxplots at each time point should be used to determine whether the response variable (on the y-axis) appears to indicate differences between the categories (on the x-axis) of the categorical predictor.
- For continuous predictors of interest, scatter plots at each time point should be used to determine whether a relationship between the response variable (on the y-axis) and the predictor variable (x-axis) is evident.

The purpose of the above steps is to investigate the relationship between the predictor variable and the given response variable.

7.3 Statistical Analyses

Primary hypothesis analysis

If comparison between the HUI3 multi-attribute score from pre-surgery to only one follow-up time point is of interest then paired t-tests can be used. A check of the assumption that the change from pre-surgery is normally distributed should be performed. The distribution of change scores should be approximately symmetric. The disadvantage of this approach is that it uses only complete data at any given pair of time points

If all pairwise differences are of interest (as per the hypothesis) and the scatter plot of change over time appears (close to) linear then a linear mixed-effects model with a fixed effect of time (treated as a continuous variable) and a random effect for participant should be used to explain the change in response variable over time. Tukey pairwise differences between time points can be specified (we recommend using the *multcomp* package in R as it does not require balanced designs i.e. the same sample size across time points). Appropriate diagnostic checks of the linear mixed-effects model (for example, normality of the residuals, normality of the random effects) should always be undertaken. An advantage of the linear mixed-effects model is that it uses all available data even for subjects who have dropped out at a given time point and then returned.

If the change over time was evidently not linear from the scatterplot of response against time then alternative approaches should be used. For example:

1. A quadratic or cubic term for time could be added to the linear mixed-effects model and checked to determine if that improves the fit of the model (eg via reduced AIC, better diagnostic checks).
2. The pre-surgery HUI3 multi attribute score value can be used as a predictor variable (with the response variable then only including the post-surgery visits). A significant coefficient would imply that the amount of change is dependent on the pre-surgery score. An interaction between baseline score and post-surgery time points could also be included – this would show whether the change in mean score over time is impacted by baseline score. This approach will remove any participant without baseline data from the analysis.
3. Use visit as categorical variable. This essentially fits a linear model between time points but makes no assumption that the change from baseline is linear. Tukey pairwise comparisons between all pairs of time points (if time is found to be a significant predictor) are straight forward with this approach and should be undertaken using the *multcomp* package in R, which does not require balanced designs.

Secondary hypotheses analysis

The approach described for the primary hypothesis can be used for all continuous responses described in the secondary hypotheses. Failure of the assumptions may indicate that that a linear model is not appropriate and that other response distributions need to be explored. At this stage it is likely best that a statistician is consulted.

For ordinal responses such as the CAP II score an ordinal mixed-effects model including time as a fixed effect and participant as a random effect. The results of this model will show the

odds of being in a higher category compared to the current category over time (this interpretation is package dependent).

Tertiary hypotheses analysis

The approach described for the primary hypothesis is appropriate here also for continuous outcomes. As described above, for ordinal responses an ordinal mixed-effects model including time as a fixed effect and participant as a random effect. If the response variable is nominal (categorical without natural ordering) a multinomial mixed-effects model can be used and for binary responses a mixed effects logistic regression can be undertaken.

If only one pair of time points is of interest then for binary responses a test for the change in proportions can be undertaken and for continuous responses a paired t-test can be undertaken.

Analysis for other hypotheses

The other hypotheses involve the effect of covariates on a response and on the change over time. To assess the effect of a given covariate (for example age, gender, etc) the covariate can be added to the model as a fixed main effect in addition to the time variable and as an interaction with the time variable.

While there is no widely accepted standard approach for creating a statistical model, in the situation where many covariates are of interest, one approach is to use a model that includes only one covariate at a time (in addition to time) and assess its significance. Combinations of covariates with p-values less than 0.1 could then be added to the model at the same time (eg age and gender). Finally, those without significant p-values at the 5% level could be removed from the final model. If an interaction is significant but the main effect for that covariate is not significant, the main effect should be retained in the model. If an interaction is not significant it can be removed from the model.

For each covariate included in the model a rule of thumb suggests having at least 20 participants. In other words, if the sample size is 100 participants then a maximum of 4 covariates plus time could be included in the model. This approach aims to retain sufficient power to find a significant result if an association between these variables indeed exists.

